4. STUDY DESIGN

4.1. Design

The Novoglan-01 clinical trial is an investigator-initiated, single arm, non-randomised, observational, prospective study.

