6.8. End of Study Treatment

At the end of a Novoglan-01 study and during the Final Study Visit, each participant will be:

- Measured for phimosis using the same measuring scale as used during Visit 1
- Surveyed for any adverse effect experienced during the study and not as yet reported
- Surveyed for quality of life using the same questionnaire as used during Visit 1
- Surveyed for tolerability of treatment using a purpose-designed questionnaire

Finally, at the end of each participant Final Study visit, all clinical trial documents related to the participant will be collected and stored in the ***Clinical Trial Master File*** for subsequent analysis and storage as per guidelines from the Australian Clinical Trial Handbook Version 2.0 dated March 2018.

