8.2. Detailed Analysis Plan

The Novoglan-01 clinical trial involves the following measurement variables, which will be measured pre- and post-treatment:

Primary outcome variable (ordinal, scalar): Kikiros-inspired phimosis assessment scale (Kikiros, Beasley & Woodward 1993)

Secondary outcome variable (ordinal, scalar): A standardized treatment tolerability questionnaire

Secondary outcome variable (ordinal, scalar): A QoL scale questionnaire

The trial will also involve descriptive variables collected for each patient:

Physical parameters (e.g. age, weight, height – numerical variables)

Medical history (categorical, binary)

Record of Adverse Events (categorical, binary)

Evaluating Patient Descriptive Variables

The recommended analysis plan for the descriptive variables is to use a univariate analysis to contribute to the descriptive statistics of N. From there, tables showing frequency with medians, range, and standard deviations can be generated to describe the population.

Evaluating the Primary and Secondary Outcome Variables

An initial validation of each primary and secondary outcome variable will be applied using the Principal Component Analysis. If this analysis is successful, then each variable will be evaluated in an ordinal regression model (De Leeuw, Mair & Groenen 2017). If the outcome variables are to be evaluated at the same time, then a Multivariate Multinomial Logit Model will be applied (Bel & Paap 2014).

Further tests may be applied to evaluate any distributions and homogeneity within and between descriptive and outcome variables such as a Chi-Squared Test, Linear-by-linear Association Test, or Mann-Whitney U Test.

REFERENCES

- Bel, K. & Paap, R. 2014, A Multivariate Model for Multinomial Choices.
- R Development Core Team 2017, *R: A Language and Environment for Statistical Computing*, Vienna, Austria., R. Found. Stat. Comput., vol. 1.

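### Section 8.2 names no analysis in a form that uses the before/after pairing of phimosis grade and quality of life in this single-arm trial

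*Protocol*

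**What the plan says.** Protocol Section 4.1 describes a "single arm, non-randomised, observational, prospective study". Section 4.4 makes the primary endpoint the improvement in foreskin retraction on a phimosis scale. Section 6.8 has each man, at the Final Study Visit, "Measured for phimosis using the same measuring scale as used during Visit 1", and repeats the quality of life questionnaire from the same visit.

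Section 8.2 introduces its primary and secondary variables as ones "which will be measured pre- and post-treatment" and classes the main one as "Primary outcome variable (ordinal, scalar): Kikiros-inspired phimosis assessment scale". It then names these methods:

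- **Ordinal regression** of each variable, if a principal component analysis used as validation succeeds. No model terms are given.
- **Multinomial logit**, if the outcomes are analysed together: "then a Multivariate Multinomial Logit Model will be applied".
- **Optional further tests** of distributions and homogeneity, within and between descriptive and outcome variables: "such as a Chi-Squared Test, Linear-by-linear Association Test, or Mann-Whitney U Test".

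Section 8 presents this as a summary of the main points of a separate Statistical Plan, which is not at hand.

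**The concern.** With one arm, the only treatment contrast is each man's final value against his own baseline. An analysis of that contrast must use the pairing, either through differences, through adjustment for baseline, or through a participant effect. Section 8.2 names several methods and states none of them in such a form. It names no method made for paired ordinal data, such as a signed-rank, sign or marginal homogeneity test.

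Two things are at stake. First, if the two sets of readings were compared as independent samples, the standard error would be wrong: too large when a man's two readings correlate positively, too small when they correlate negatively. Second, with several candidate methods and no single paired one fixed, the primary result depends on a choice that could be made after the data are seen, in an open-label trial.

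**Working it through.** **1. Which outcomes are paired.** The visit table in 6.2, with 6.8 and 7.1, puts phimosis grade and quality of life at both Visit 1 and the Final Study Visit. The tolerability questionnaire appears at the Final Study Visit only. So two outcomes are paired, and the lead sentence of 8.2 is wrong about tolerability.

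**2. What each named method does with the pairing and the ordering.**

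| Method in 8.2 | Status | Pairing | Ordering |
|---|---|---|---|
| Ordinal regression | main route, after the principal component step | not stated; possible | used |
| Multinomial logit | only if outcomes are analysed jointly | not stated | discarded |
| Chi-squared | optional | ignored in standard form | discarded |
| Linear-by-linear | optional | ignored in standard form | used |
| Mann-Whitney U | optional | ignored | used |

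**3. Size of the multinomial model.** The protocol gives no number of levels, so 4 to 6 per outcome is assumed. Three outcomes give 3 × (4 − 1) = 9 to 3 × (6 − 1) = 15 intercepts, plus another 9 to 15 coefficients for each covariate, for 24 men. Ordinal models have as many thresholds but need one slope per covariate per outcome, so 3.

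**4. The plan's own figure.** Section 8.1 gives N = 24 and 29 recruited at 20% drop-out. Only the drop-out step can be checked: 24 × 1.2 = 28.8, rounded up to 29 (24 / 0.8 would give 30). N = 24 itself cannot be reproduced, because the protocol states no significance level, power, effect size or variance.

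**5. Consequence if an unpaired test were used for the before/after change.** For a normal outcome with before/after correlation ρ, the actual two-sided type I error of an unpaired test at nominal 5% is

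2 × [1 − Φ(1.96 / √(1 − ρ))].

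- ρ = 0: 5.0%
- ρ = 0.3: 1.96 / √0.7 = 2.34, giving 1.9%
- ρ = 0.5: 1.96 / √0.5 = 2.77, giving 0.6%
- ρ = 0.7: 1.96 / √0.3 = 3.58, giving 0.03%

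The ordinal case was simulated. Assumptions, none of them from the protocol except n: 24 pairs, a latent normal variable cut into six grades equally likely at baseline, two-sided 5%, 3,000 simulated trials per setting. Entries are rejection rates in % for signed-rank / Mann-Whitney / chi-squared.

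| ρ | no effect | shift 0.5 SD | shift 0.8 SD | shift 1.5 SD |
|---|---|---|---|---|
| −0.3 | 5.0 / 8.5 / 5.4 | 29.0 / 37.6 / 20.7 | 58.8 / 69.0 / 44.5 | 97.9 / 99.0 / 93.4 |
| 0 | 5.0 / 5.3 / 4.6 | 33.9 / 36.1 / 17.0 | 70.4 / 73.2 / 44.3 | 99.4 / 99.7 / 94.8 |
| 0.3 | 4.7 / 2.3 / 3.5 | 43.0 / 32.8 / 14.4 | 82.4 / 74.9 / 40.4 | 99.9 / 99.7 / 96.0 |
| 0.5 | 3.9 / 0.6 / 2.2 | 55.2 / 31.1 / 11.4 | 91.7 / 79.3 / 42.5 | 100 / 100 / 96.8 |
| 0.7 | 4.6 / 0.0 / 1.6 | 73.1 / 26.5 / 9.4 | 98.4 / 81.2 / 37.6 | 100 / 100 / 98.3 |

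At a shift of 0.6 SD, separate runs of 4,000 and 2,000 trials gave signed-rank against Mann-Whitney power of 72% to 73% against 47% to 50% at ρ = 0.5, and 88% to 90% against 48% at ρ = 0.7. Ordinal regression and the linear-by-linear test were not simulated.

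**The case against.** The strongest reply is that 8.2 does not commit to a wrong test. Several parts of it stand.

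- A reader might infer that the primary change will be tested with Mann-Whitney or chi-squared. The text does not say so: those tests are optional and are tied to distributions and homogeneity, not to the primary change.
- A reader might infer that these tests have no second group to compare. They do: two hospitals (4.5), men with and without Balanitis Xerotica Obliterans or prior frenuloplasty (5.1), and the binary history and adverse event variables in 8.2.
- A reader might take every outcome to be before/after, as 8.2 says. The schedule contradicts that for tolerability.
- The ordinal regression could use the pairing, for example with final grade regressed on baseline grade. Silence about its terms does not show that it treats readings as independent, and the unseen Statistical Plan may give the form.
- The multinomial logit is conditional, and its parameter count rests on assumed numbers of levels.
- Section 1 of the protocol anticipates full normal retraction. If the effect on phimosis grade is that large, the choice between signed-rank and Mann-Whitney hardly affects power.

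This does not remove the point. Section 8.2 is headed as a detailed plan and chooses to name methods. The methods it names outright either lack a stated paired form or do not suit the contrast that defines the primary endpoint.

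**Conclusion.** The point holds as a defect of specification: for phimosis grade and quality of life, 8.2 states no analysis in a form that uses the pairing. It is not shown that the primary endpoint will be tested wrongly.

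The size depends on a correlation and an effect that the protocol does not give, and the power figures apply only if an unpaired test is used for the before/after change. Under the simulation assumptions:

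- **Positive correlation:** Mann-Whitney is conservative and loses power. At ρ = 0.5 its type I error is about 0.6% to 1%, and at shifts of 0.5 to 0.6 SD its power is about 31% to 50%, against 55% to 73% for signed-rank.
- **Zero correlation:** Mann-Whitney loses nothing. Chi-squared still loses about half the power at 0.5 SD (17% against 34%), because it ignores ordering.
- **Negative correlation:** Mann-Whitney type I error is inflated, to about 8.5% at ρ = −0.3.
- **Very large effect (1.5 SD):** signed-rank and Mann-Whitney both reach about 98% or more.

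The practical loss would therefore fall mainly on modest effects, which may be the case for quality of life. Separately, the multinomial logit contradicts the ordinal status that 8.2 gives its outcomes and is likely too heavily parameterised for 24 men.

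**What to change.** In Section 8.2, and in the Statistical Plan to match:

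1. Name one paired ordinal primary analysis of Final minus Visit 1 phimosis grade. The Wilcoxon signed-rank test is one option; the sign test avoids treating steps between grades as comparable in size; a cumulative-logit model with a time term and participant effect is another.
2. Report the change, and the proportion of men improving by at least one grade, each with a 95% CI.
3. Use the same method for quality of life.
4. Correct the lead sentence so that tolerability is a post-treatment-only measure, summarised descriptively.
5. Replace the multinomial logit with models that respect ordering.
6. Limit the chi-squared, linear-by-linear and Mann-Whitney tests to exploratory comparisons between subgroups.

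The cost is wording and minor analysis work. No additional data or visits are needed, and standard software suffices. If the Statistical Plan already specifies a paired form, copying it into 8.2 settles items 1 to 3.

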9. DATA COLLECTION

9.1. Participant Registration

Participant registration in the Novoglan-01 study will be documented using the **Case Report Form** completed during the Enrolment Visit. Following execution of the Participant Information and Consent Form at the Enrolment Visit, the participant will be allocated a unique participant identifier that will figure in all documents relating to that particular participant and the enrolment will be logged in the Novoglan-01 Participant Enrolment Registry.

9.2. Forms and Procedure for Collecting Data

During the study, all information collected about the Participant will be compiled in an individual Participant Case Report Form Folder (ring binder) containing the Case Report Forms and related documents.

Novoglan-01 Case Report Form Folders will be kept in a dedicated lockable filing cabinet at the study site as part of the Trial Master File.

The Novoglan-01 study data collection forms and documents are listed as follows.

- Novoglan-01 **Clinical Data Management Plan**
- Novoglan-01 **Participant Information and Consent Form (PICF)**
- Novoglan-01 Trial Participant Enrolment Registry included in the Recruitment Plan
- Participant Unique Identifier – Included in Participant Enrolment Registry
- Participant Compensation Log included in the Recruitment Plan
- Potential Participant Contact Registry included in the Recruitment Plan
- Novoglan-01 **Participant Case Report Forms Folder** for all study visits and including the Participant Withdrawal Form
- Novoglan-01 **Clinical Trial Research Agreement (CTRA)**
- Novoglan-01 – **Product Liability Insurance** certificate / cover letter
- Novoglan-01 clinical trial – MQ **Clinical Research Governance** approval
- Novoglan-01 – **HREA form**
- Novoglan-01 MQ Final HREC approval
- Novoglan-01 **Investigator Brochure (IB)**
- Novoglan-01 Investigator Site File (ISF)
- Novoglan-01 **Clinical Trial Protocol**
- Novoglan-01 **IP Manual** with Novoglan User Instructions and Illustrated User Guide
- Novoglan-01 **Recruitment Plan**
- Novoglan-01 **Safety Plan**
- Novoglan-01 **Statistical Plan**
- Novoglan-01 **Clinical Team CV's**
- Novoglan-01 Study Phimosis Measurement Form included in Participant CRF Folder
- Novoglan-01 Study Health-Related Quality of Life Questionnaire included in Participant CRF Folder
- Novoglan-01 Treatment Tolerability Questionnaire included in Participant CRF Folder
- Novoglan-01 **Participant Withdrawal Form** included in Participant CRF Folder

9.3. Case Report Forms and Schedule for Completion

The Case Report Forms to be used during the Novoglan-01 study are contained in the **Novoglan-01 Participant Case Report Form Folder**. They are listed in Section 9.2 and attached to this protocol. The paper format of all the Case Report Forms and their layout have been designed to facilitate completion of the CRF during each Study Visit by the Principal Investigator and the Clinical Trial Nurse or at most within 2 working days following the Study Visit. All Case Report Forms are to be compiled in the individual Participant Case Report Forms Folder, set up at enrolment for each study participant and based on a blank folder kept in a ring binder in the lockable filing cabinet at the trial site containing the Clinical Trial Master File.

9.4. Data Flow

The Case Report Forms, questionnaires and all other study documents relating to a particular participant will be provided blank and collected once completed in 12 ring binders, each corresponding to a particular participant. Additional ring-binders will be used should

the study cohort exceed 12 participants. These ring binders will be kept in a lockable cabinet at the trial site and constitute part of the Novoglan-01 Trial Master File.

The access to the Study Data is strictly limited to the research team which includes [name] and [name] as study investigators, [name] and [name] as study research nurses, [name] and [name] as study investigator assistants and [name] as study biostatistician. On conclusion of the study when 24 participants have been accrued and on advice from [name], [name] will collate all Participants Folders and transfer the required information from the Case Report Forms into an Excel Novoglan-01 study spreadsheet prepared and communicated to [name] by [name]. To ensure correct transfer of data, [name] will review the correctness of the data transfer information from the Participant Folders into the Excel Novoglan-01 study spreadsheet. On receipt of the Excel Novoglan-01 study spreadsheet, [name] will carry out the statistical analysis that concludes the Novoglan-01 study.

10. QUALITY CONTROL AND ASSURANCE

10.1. Control of Data Consistency

The control of data consistency for the Novoglan-01 clinical trial is detailed in the Novoglan-01 **Clinical Data Management Plan**, attached to this Study Protocol, the main sections of which are as follows.

- Investigator Site File (ISF)
- Participant Case Report Form Folders
- Protocol Amendments
- Site Initiation Visit (SIV)
- SIV Training and Training Certificates
- Trial Activation Audit and Monitoring Report
- Trial Master File – Confidentiality, storage and archiving of study data
- Trial Master File – Set-up audit report and trial completion audit report

10.2. Audits

As **detailed in the Novoglan-01 Clinical Data Management Plan**, the audit schedule for the Novoglan-01 trial is as follows.

- Trial Activation – Audit and Monitoring Report
- Trial Master File Set Up – Audit and Monitoring Report
- Trial Master File at study completion - Audit and Monitoring Report

10.3. Protocol Amendments

As detailed in the Novoglan-01 Clinical Data Management Plan, Protocol Amendments will be recorded, processed and compiled in the Investigator Site File.

11. ETHICS

11.1. Investigator Authorisation Procedure

As an Investigator Initiated Study, a CTN notification will not be required for the Novoglan-01 study. However, a Clinical Trial Research Agreement will be prepared by the parties to this Novoglan-01 Investigator Initiated Study: Macquarie University as the Institution and Platigo Solutions, the supplier of the Novoglan investigational product, as the Organisation. ***An executed copy of the Novoglan-01 CTRA is attached to this Study Protocol.***

In order to comply with the ethical rules applicable in Good Clinical Practice and Macquarie University policies in that matter, the Novoglan-01 study core documentation (Protocol, Investigator Brochure, Participant Information and Consent Form, Clinical Trial Research Agreement, Statistical Plan, Recruitment Plan, Safety Plan, Clinical Trial insurance cover letter and all Case Report Forms with related appendices such as questionnaires) will be submitted successively for review to:

- The Macquarie University Clinical Research Governance for initial review.
- The Macquarie University Clinical Research Governance for final governance authorisation review
- The Macquarie University Human Research Ethics Committee (HREC) for review.

Upon satisfactory completion of these reviews and authorisations to proceed with the Novoglan-01 study by the Macquarie University Human Research Ethics Committee, the Novoglan-01 study will be registered in the Australian government Clinical Trials database and the study will commence its implementation phase.

Additionally, and on the direction of Principal Investigator [name] in a Note-To-File dated 15 September 2020, it has been decided that all research team staff at Macquarie University ([name], [name], [name], [name]) and at Princess Alexandra Hospital (Associate [name], [name], [name]) will sign a declaration committing to the unbiased analysis of the study results and the publication of the study results.

11.2. Participant Protection

As Principal Investigator, [name] will ensure that the study is completed in accordance with the guidelines set out in the National Statement on Ethical Conduct in Human Research (2007) (the National Statement) and the CPMP/ICH Note for Guidance on Good Clinical Practice and any other relevant legislation/guidelines.

12. SAFETY

12.1. Adverse Event Reporting

The Novoglan product is a medical device, not a therapeutic product. As such, any adverse event encountered during the Novoglan-01 clinical trial should be recorded and processed as per the ***Therapeutics Goods Administration IRIS Reporting Scheme*** applicable to medical devices and which is detailed in the ***Novoglan-01 Safety Plan*** attached to this Study Protocol.

Devices Adverse Events - Definition

Any undesirable clinical occurrence in a participant whether it is considered to be device related or not, that includes a clinical sign, symptom or condition and/or an observation of an unintended technical performance or performance outcome of the device.¹

For devices is any adverse medical occurrence that:

- led to a death;
- led to a serious deterioration in health of a participant, including:
 - a life-threatening illness or injury;
 - a permanent impairment of body function or permanent damage to a body structure;
 - a condition requiring hospitalisation or increased length of existing hospitalisation;
 - a condition requiring unnecessary medical or surgical intervention; or
 - foetal distress, foetal death or a congenital abnormality/birth defect;
- might have led to death or a serious deterioration in health had suitable action or intervention not taken place. This includes:
 - a malfunction of a device such that it has to be modified or temporarily/permanently taken out of service; or
 - a factor deterioration in characteristics or performance) found on examination of the device.

An adverse event or serious adverse reaction can also be any event or experience which compromises the ethical acceptability of the protocol. This can be a non-medical event for clinical trials that are not medical or testing drugs or devices, such as those clinical trials conducted in different fields such as psychology.

12.2. Serious Adverse Event Reporting

Any serious adverse events occurring during the Novoglan-01 study will be recorded and reported as per the ***Therapeutics Goods Administration IRIS Reporting Scheme*** applicable to medical devices and which is detailed in the ***Novoglan-01 Safety Plan*** attached to this Study Protocol. Any serious adverse event will be immediately reported by the Principal Investigator, [name], to the Macquarie University HREC. The reports should be followed by a detailed written report. Follow-up reports should identify the participant/s by unique code assigned to participants (rather than by name).

¹ Ibid.

12.3. Data Safety and Monitoring Committee (DSMC)

Following advice from the Macquarie University Clinical Research Manager, the Novoglan-01 study will not require the appointment of a DSMC.

12.4. Early Termination

Aside from an injunction from Macquarie University HREC, there are several possible cases where the Novoglan-01 clinical trial could be prematurely terminated, such as:

- Administrative reasons – An organisation with administrative control over the study decided to terminate it.
- Change in practice – Methods or practices have changed in a way that alters the necessity or practicality of the study - Example: Manufacturing change in one of the two types of balloons used in the Novoglan device pack
- Change in study design – The study protocol needs to be altered – Example: Trial suspended pending approval of an amended protocol.
- Enrolment completed – The goal for 12 participants to be recruited has been achieved.
- Resources – Materials or personnel required for the study could not be obtained. – Example: Temporary suspension until resources supply resumes.
- Insufficient enrolment – Not enough participants enrolled in the study – Example: termination due to lack of participant recruitment.
- Key staff departure – A critical member of the clinical team has left the study.
- Non-compliance – Either the participants or the investigators failed to follow the study protocol – Example: Inability to keep participants following the treatment protocol.

In fairness and in view of the commercialisation track record of the Novoglan product, any of these possibilities can be seen as very unlikely. However, if the Novoglan-01 clinical trial needs to be terminated early, then:

- The Sponsor (Macquarie University) and the Macquarie University HREC will be immediately informed of the situation and any planned remediation.
- The participants in the study will be informed of the situation and of any planned remediation.
- If the study cannot resume, the final study report will be compiled.

